APPENDIX A: ANALYSIS WINDOWS

Table 1.1 Analysis	Visit Window for	Selected ePRO En	dpoints (Dail	y for First Six Weeks)
--------------------	------------------	------------------	---------------	------------------------

Analysis Visit	Target Analysis Day	Low Analysis Day	High Analysis Day
Day 1/Baseline	1		1
Day 2	2	2	2
Day 42	42	42	42
Week 7	50	43	49
Week 23	162	156	162
Week 24	169	163	

Table 1.2 Analysis Visit Window for Selected ePRO Endpoints (Weekly for First Six Weeks)

Analysis Visit	Target Analysis Day	Low Analysis Day	High Analysis Day
Day 1/Baseline	1		1
Week 1	8	2	8
Week 2	15	9	15
Week 3	22	16	22
Week 4	29	23	29
Week 5	36	30	36
Week 6	43	37	43
Week 7	50	44	50
Week 23	162	156	162
Week 24	169	163	

Table 2. Analysis Visit Window for EQ-5D-Y Proxy Version 1, EQ-5D-Y and EQ-5D-5L

Analysis Visit	Target Analysis Day	Low Analysis Day	High Analysis Day
Day 1/Baseline	1		1
Week 1	8	2	8
Week 2	15	9	15
Week 3	22	16	22
Week 4	29	23	29
Week 5	36	30	36
Week 6	43	37	43
Week 8	57	51	57
Week 12	85	79	85
Week 16	113	107	113
Week 24	169	163	

Table 3. Analysis Visit Window for Viral Load (in Blood and Urine), Vital Signs, Pulse Oximetry, Clinical Chemistry and Hematology

Analysis Visit	Target Analysis Day	Low Analysis Day	High Analysis Day
Day 1/Baseline	1		1
Week 1	8	2	11
Week 2	15	12	18
Week 3	22	19	25

Analysis Visit	Target Analysis Day	Low Analysis Day	High Analysis Day
Week 4	29	26	32
Week 5	36	33	39
Week 6	43	40	63
Week 12	85	64	126
Week 24	169	>126	

Table 4. Analysis Visit Window for 12-Lead ECG and Weight

Analysis Visit	Target Analysis Day	Low Analysis Day	High Analysis Day
Day 1/Baseline	1		1
Week 2	15	2	92
Week 24	169	>92

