These assessments will be administered at baseline, weekly through Week 6, and then at Weeks 8, 12, 16, and 24.

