3 STATISTICAL METHODOLOGY

3.1 General Considerations

3.1.1 Study Day from Randomization

Study day will be calculated from the date of randomization, as analysis day = actual assessment/collection/visit date – randomization date (+1 for dates on or after the randomization date and not for dates before the randomization date). All the efficacy endpoints will be summarized at and post randomization based on the study day from randomization.

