3.1.3 Analysis Visits

All the visits will be assigned to analysis visits according to the visit windows indicated by analysis windows of this SAP (Appendix A). If two or more visits fall into the same analysis window, the visit closest to the planned visit timepoint will be used. If the distances to the planned visit are equal, the latest one will be used. If multiple assessments occur on the same day, the values will be averaged. For laboratory data, if a retest visit can be identified due to result error (eg, laboratory error or physiologically improbable results) in the original test visit, the retest visit will be used in place of the original test result for that visit.

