Time to resolution of BK viruria will be analyzed using Kaplan-Meier estimates, and treatment effect will be compared using stratified log-rank test and hazard ratio with stratified Cox proportional model. Resolution of viruria is defined by the lower limits of quantitation of the assay used. Resolution of viruria is defined by the lower limits of quantitation of the assay used. Only the participants who had BK viruria at randomization will be included in the analysis. Time to resolution refers to the time from randomization to the initial resolution of viruria.

The numbers and proportions of patients with viremia and viruria with each target virus (ie, BKV, AdV, CMV, HHV-6, JCV, and/or EBV) over time for all the participants as well as for participants who are negative at randomization only.

Length of use of any pain medication(s) (IV, oral, or other), including antispasmodics anticholinergics, and beta-3-agonists, used for control of lower abdominal/bladder pain will be summarized as the total days on any pain medication for each participant.

The use of immunosuppressive agent(s) by specific agent during the study will be summarized by treatment group. The specific dosage information will be listed only.

Number of hospitalizations, number of ICU stays, and number of days of ICU care for any reason will be summarized by treatment group, and reasons will be listed by participant.

Use of antiviral therapies other than cidofovir with potential activity against at least one target virus will be summarized by specific agent during the study. Agents analyzed include foscarnet, ganciclovir, letermovir, maribavir, and valganciclovir. Rd

Overall survival, defined as time to death (from any cause) from the time of randomization in days, will be analyzed as displaying number of participants who died from any cause by week 24 and censored by week 24.

Incidence of relapse or progression of the primary malignancy will also be summarized by treatment group over the 24-week period.

Overall quality of life as measured by appropriate EQ-5D questionnaires will be summarized by treatment for each subdomain over time.

Global impression of change will be summarized by treatment over time.

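### SAP Table 2 leaves gaps between the EQ-5D windows after Weeks 6, 8, 12 and 16, so a form one day late at those visits has no analysis visit

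*SAP*

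**What the plan says.** Protocol 7.2.7 sets the EQ-5D schedule: "These assessments will be administered at baseline, weekly through Week 6, and then at Weeks 8, 12, 16, and 24". SAP Appendix A, Table 2 ("Analysis Visit Window for EQ-5D-Y Proxy Version 1, EQ-5D-Y and EQ-5D-5L") has a row for each of these visits, so no visit is missing. A typical row, giving target, low and high day, is "Week 12 85 79 85".

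SAP 3.1.3 governs how dates become visits: "All the visits will be assigned to analysis visits according to the visit windows indicated by analysis windows of this SAP (Appendix A"). Its selection rule covers only competing records inside one window: "If two or more visits fall into the same analysis window, the visit closest to the planned visit timepoint will be used". It does not say what happens to a date outside every window.

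Days are counted from randomization: "All the efficacy endpoints will be summarized at and post randomization based on the study day from randomization". Randomization is Day 1. The analysis depends on the assigned visits: "Overall quality of life as measured by appropriate EQ-5D questionnaires will be summarized by treatment for each subdomain over time". SAP 3.1.7 says that efficacy data are in general analyzed as observed, without imputation.

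Table 3 of the same appendix ("Analysis Visit Window for Viral Load (in Blood and Urine), Vital Signs, Pulse Oximetry, Clinical Chemistry and Hematology") uses windows that touch one another. So does Table 4, for ECG and weight.

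**The concern.** A visit window should collect the record meant for that visit even when it is a little early or late. The Table 2 windows reach back six days but not forward at all, and once the schedule stops being weekly nothing covers the days between them. A form completed the day after its target at Week 6, 8, 12 or 16 is valid data, yet the plan gives it no visit and no other route into the by-visit summary.

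Two related effects follow. In Weeks 1-5, where the windows do touch, a form one day late is relabelled as the next week. And under Protocol 4.3.1 an early-termination visit repeats the Week 24 assessments, which include EQ-5D, so a participant who leaves on a gap day completes a form that maps to no visit. What is at stake is the completeness and correct labelling of the quality-of-life summary over time.

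**Working it through.** The plan states no figure on this point, so there is none to reproduce. The check sets every study day against the Table 2 limits.

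**Inputs (SAP Appendix A, Table 2; target: low-high).** Baseline 1: up to 1. Week 1, 8: 2-8. Week 2, 15: 9-15. Week 3, 22: 16-22. Week 4, 29: 23-29. Week 5, 36: 30-36. Week 6, 43: 37-43. Week 8, 57: 51-57. Week 12, 85: 79-85. Week 16, 113: 107-113. Week 24, 169: 163 onward.

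**Step 1, targets.** With randomization as Day 1, Week k should have target 7k + 1. Week 6: 7 × 6 + 1 = 43. Week 12: 7 × 12 + 1 = 85. Week 24: 7 × 24 + 1 = 169. All rows agree, so the targets are right and only the limits are in question.

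**Step 2, days in no window.**

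| Gap | Days | Count |
|---|---|---|
| Week 6 to Week 8 | 44-50 | 7 |
| Week 8 to Week 12 | 58-78 | 21 |
| Week 12 to Week 16 | 86-106 | 21 |
| Week 16 to Week 24 | 114-162 | 49 |
| Total | | 98 |

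98 / 168 = 58.3% of Days 1-168. As a cross-check, the gaps are the weekly slots for Weeks 7, 9-11, 13-15 and 17-23: (1 + 3 + 3 + 7) × 7 = 98. Table 2 therefore looks like a weekly grid from which the unscheduled weeks were removed without widening the rest.

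**Step 3, one day late.**

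| Form due | Completed on day | Assigned to |
|---|---|---|
| Weeks 1-5 | 9, 16, 23, 30, 37 | Next week |
| Week 6 | 44 | None |
| Week 8 | 58 | None |
| Week 12 | 86 | None |
| Week 16 | 114 | None |
| Week 24 | 170 | Week 24 |

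In Weeks 1-5 the closest-to-target rule then works against the late form. A Week 2 form on Day 16 competes for the Week 3 target of Day 22. It is dropped if the Week 3 form is nearer to Day 22, and is reported as Week 3 if there is no other form in that window.

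**Step 4, Week 6 against the protocol.** Protocol Appendix B shows ±3 days for six post-baseline columns, read here as Weeks 1-6. Week 6 is protocol Day 42, so the permitted range is protocol Days 39-45, or SAP Days 40-46. Days 40-43 map to Week 6; Days 44-46 map to nothing. Three of the seven permitted days are unassigned.

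**Step 5, comparator.** The same enumeration on Table 3 leaves 0 days unassigned. Its windows for Weeks 2-5 are the target ±3 (for example Week 2, target 15: 12-18), which match the Appendix B allowance.

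**The case against.** The best defence is that the seven-day window ending on the target is a deliberate convention. Table 1.2 uses it for weekly instruments, and narrow windows protect timing. Table 3 covers samples and measurements taken at clinic visits with wide windows, so it is not a like-for-like benchmark. Part of this stands: width is a trade-off. But in Table 1.2 the weekly windows touch (taking the rows between Weeks 7 and 23 to continue the pattern). In Table 2 they do not, and the SAP gives neither a reason nor a rule for the gaps.

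Four stronger readings are tempting, and the documents do not support them.

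- **That 58% of EQ-5D data would be lost.** The 98 days are calendar days, on most of which no form is due; 49 of them lie between Weeks 16 and 24. Loss depends on how many forms are late, which the documents do not give. Protocol 7.2 provides a hand-held device, with paper as back-up, and does not say whether late entry is blocked.
- **That only 7 of 57 permitted days count for Week 12.** This applies the clinic visit's ±28 days (SAP Days 57-113) to EQ-5D. Protocol Appendix A refers these instruments to Appendix B, which shows no window for Weeks 8-24. Appendix C lists no clinic sampling visit at Week 8 or 16. Applying ±28 days is an assumption.
- **That the lost forms are those of sicker participants.** This is plausible, particularly for early terminations, but nothing in the documents establishes it.
- **That the SAP orders late forms to be discarded.** It does not say so. Omission from the summary follows from having no visit and no fallback; the record may still be listed.

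**Conclusion.** The point holds, and it is minor. Followed as written, SAP 3.1.3 and Table 2 leave out of the by-visit EQ-5D summary any form completed one day late at Week 6, 8, 12 or 16 and any early-termination form completed on a gap day. They also shift late Week 1-5 forms by one week. The day counts are exact. Week 24 is not affected by lateness, because its window has no upper limit.

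The firmest conflict is at Week 6, where three days that the protocol permits have no visit. That rests on two assumptions: that the six ±3 columns in Appendix B are Weeks 1-6 and govern the weekly EQ-5D entry, and that randomization and first infusion fall on the same day, as the protocol's schedule has it. If infusion came a day later, forms exactly on time by the infusion date would land one day past target.

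How many forms would be affected is unknown. EQ-5D is an exploratory endpoint, summarized descriptively and outside the testing hierarchy, so the primary, key secondary and hospital-days tests are untouched.

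**What to change.** Replace the Table 2 limits with contiguous windows cut at the midpoints between targets, and keep the closest-to-target rule in SAP 3.1.3.

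| Visit | Target | Window | Midpoint with next target |
|---|---|---|---|
| Weeks 1-5 | 8-36 | As in Table 3 | |
| Week 6 | 43 | 40-50 | (43 + 57) / 2 = 50 |
| Week 8 | 57 | 51-71 | (57 + 85) / 2 = 71 |
| Week 12 | 85 | 72-99 | (85 + 113) / 2 = 99 |
| Week 16 | 113 | 100-141 | (113 + 169) / 2 = 141 |
| Week 24 | 169 | 142 onward | |

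This leaves 0 of 168 days unassigned, and a form one day late stays with its own visit.

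The cost is looser timing, which is not negligible against windows that now span seven days. A Week 16 record could be 141 − 113 = 28 days after target, and a Week 24 record 169 − 142 = 27 days before it. At Weeks 8 and 12 the largest distance is 14 days. If the sponsor prefers narrow windows, SAP 3.1.3 should at least state how a record outside every window is handled, including early-termination forms. Either change is an edit to the SAP that should be made before database lock. It needs no new data and alters no test or significance level.
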